# **Background and Introduction**

Cystic fibrosis related diabetes (CFRD) is the most common extra-pulmonary comorbidity in patients with cystic fibrosis (CF). CFRD is also associated with accelerated decline in pulmonary function, increased pulmonary exacerbations and increased mortality. Continuous glucose monitoring (CGM) involves the use of a small disposable sensor sited in the subcutaneous interstitial fluid that makes frequent glucose measurements. There is data suggesting that the Medtronic iPro continuous glucose monitors (CGM) can predict hemoglobin a1c levels in patients with CFRD.

The aim of our study is to assess the utility of CGMs to determine the optimal method to dose meal-time insulin. We will examine glucose excursions in patients with CF who will dose meal-time rapid acting insulin by carbohydrate counting versus fixed dose rapid acting insulin. The carbohydrate ratio and fixed doses will be determined by existing doses, total daily insulin doses, body weight and insulin sensitivity along with predisposition to hypoglycemia. Bolus insulin dosing is an important part of CFRD management due to the high nutritional demands on these patients. If dosed incorrectly, this could lead to marked hyperglycemia and could worsen nutritional status due to urinary glucose losses. In this project, we will perform a within subjects' comparison of the 2 standard methods of meal-time rapid acting insulin dosing.

### **Hypothesis:**

- We hypothesize that postprandial interstitial fluid glucose levels in patients who utilize carbohydrate counting to dose mealtime rapid acting insulin will have improved control as defined as area under the curve and time in target compared to patients who used fixed dose mealtime insulin
- 2. Our second hypothesis is that patients who utilize carbohydrate counting will have fewer hypoglycemia events compared to patients who use fixed dose meal-time insulin

## **Specific Aims:**

- 1. To compare within-subject glucose excursions\_defined as percentage of time\_in target glucose level, percentage of glucose in target and peak post prandial glucose with fixed insulin dosing versus carbohydrate count based insulin dosing.
- 2. To compare the frequency and duration of hypoglycemia (defined as daily, weekly and average duration of event) between insulin delivery methods described above.
- 3. To test the use of 'rule of 500' for carb counting estimation in CFRD patients.
- 4. To compare the effect of two methods of rapid acting insulin delivery on fasting glycemia

# **Research Design and Methods**

## Subject population:

Adult patients with a diagnosis of CFRD will be recruited from the CF Center at the University of Pittsburgh. Sample size will be 20 patients. Inclusion criteria will be adults >18 age of years with diagnosis of CFRD (as defined by standard 2-hour oral glucose tolerance test (OGTT) Patients who are being evaluated for transplant and patients who already use CGM will be excluded. Stable lung transplant patients who are more than 1 year from transplantation will be included. The patients will be individually followed in the adult CF Endocrine clinic. Downloads and data gathering will be performed at the clinic during follow up visits.

#### Methods

CGM involves the use of a small sensor sited in the subcutaneous interstitial fluid that makes frequent glucose measurements. The Wake Forest School of Medicine Endocrinology Division (WFBSM) will provide us with Abbott Freestyle Libre CGM patches to use in our CF patients. All patients will be recruited from the UPMC adult CF Center and the CF Endocrine Clinic. The CGMs will be placed in our clinic on patients recruited from the Cystic Fibrosis center. Downloads and data gathering will be performed at our center. The project will be performed in collaboration with partners from WFBSM. There will be study design input from collaborators at WFBSM as well as statistical support if needed.

Each sensor is valid for a 2-week period of use and these sensors automatically stop gathering data beyond 14 days. Each participant will be provided carbohydrate counting education and training prior to their participation by certified diabetes educators at UPMC. During the first seven days of wear, the participants will be asked to dose their meal time rapid acting insulin by fixed dose and the next 7 days, participants will be asked to dose their meal time rapid acting insulin by carbohydrate counting. Patients will be required to maintain a paper log of their carbohydrates consumed at every meal and snacks and insulin doses given during the 2-week time frame. The CGM will record blood sugars once every minute in a blinded fashion and participants will not be aware of the CGM recording data. At the completion of the 14-day period, participants will return their CMG devices for analysis and interpretation. If they live at a distance from our office and are unable to visit us to return the device, they will be permitted to mail in the sensor along with the food and glucose logs. The data will be summarized and

Protocol Date: 8/3/2021 12:46 PM

communicated to the patients once analyzed. Patient will be required maintain fingerstick blood sugar logs. The figure below describes the various study periods:

Lead in CGM use Training by Diabetes Educator

Carbohydrate and WEEK 1: PARTICIPANTS WILL DOSE MEALTIME INSULIN WITH **FIXED DOSE SCHEDULE** 

**WEEK 2: PARTICIPANTS WILL** DOSE MEALTIME INSULIN WITH CARBOHYDRATE COUNTING

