#### Data Points:

Primary: We will be measuring postprandial excursions on continuous glucose monitoring data and the instances of hypoglycemia during the two-week timeframe of the study period

Secondary: Total carbohydrates consumed each day during the two-week time frame, total daily dose of insulin per 24 hour period (midnight to midnight) will be secondary endpoints

CGM devices can be connected to desktop machines and downloaded via a receiver. The baseline characteristics that will be collected are age, sex, race, exocrine pancreatic function status, CFTR genotype, duration of CFRD, hemoglobin A1c, renal function tests, weight and BMI. From the log, insulin doses and fingerstick glucoses will be collected. The outcome measures that will be extracted from the CGM devices to assess the effectiveness of our intervention in improving glycemic control and nutritional status will include daily glucose trends calculated by percentage of time in target interstitial fluid glucose levels level and percentage of target interstitial fluid glucose levels readings, hypoglycemia episodes, and average glucose from the 2 comparison periods. This data will be compared for statistical significance using student t-test with significance assigned to p-value less than 0.05.

The clinical endocrine fellow will collect data from each included patient by performing a Cerner and Epic (EHR) chart review. Data will be recorded on an encrypted UPMC OneDrive Microsoft excel spreadsheet with password restricted access. A list of collected data points are as follows:

- 1. Age
- 2. Sex

- 3. Race
- 4. Exocrine pancreatic function status (sufficient vs. insufficient)
- 5. CFTR genotypes
- 6. Duration of CFRD
- 7. Weight and BMI at the most recent office visit or on the day of the placement
- 8. Labs: serum creatinine and eGFR (most recent value in the last 12 months), hemoglobin a1c (the most recent value in the last 3 months, or will be performed by point of care testing at the time of the CGM device placement)
- 9. Modulator use: ivacaftor (Kalydeco), lumacaftor/ivacaftor (Orkambi), tezacaftor/ivacaftor (Symdeko), elexacaftor/tezacaftor/ivacaftor (Trikafta); start date and duration of use
- 10. Meal /snack time insulin doses from log
- 11. CGM glycemic control data (percentage of time within glycemic target)
- 12. Data from fingerstick before and after intervention
- 13. Nutritional information with carbohydrates consumed per meal/snack in grams

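### Dosing method and study week coincide for every participant, so the planned week-against-week t-test cannot by itself support a comparison of methods

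*Combined protocol and SAP*

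**What the plan says.** Under Methods, one order applies to everyone: "During the first seven days of wear, the participants will be asked to dose their meal time rapid acting insulin by fixed dose", and carbohydrate counting fills days 8 to 14 of the same 14-day sensor. The study-period diagram repeats that order. The text has no second order, concurrent control, washout, or period or day term.

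The analysis compares one week with the other within patients (Statistical Analysis). Data Points adds: "This data will be compared for statistical significance using student t-test with significance assigned to p-value less than 0.05".

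The question, however, is about methods. The second hypothesis is that "patients who utilize carbohydrate counting will have fewer hypoglycemia events compared to patients who use fixed dose meal-time insulin". The second aim is "To compare the frequency and duration of hypoglycemia (defined as daily, weekly and average duration of event) between insulin delivery methods described above".

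Three further features of Methods bear on the point:
- Training comes before either week: "Each participant will be provided carbohydrate counting education and training prior to their participation".
- The sensor is masked: "The CGM will record blood sugars once every minute in a blinded fashion and participants will not be aware of the CGM recording data".
- Participants still see their own fingerstick readings: "Patient will be required maintain fingerstick blood sugar logs". They also log carbohydrates and insulin in both weeks.

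**The concern.** Using patients as their own controls removes stable differences between patients. It does not remove a change over time that the patients share. Here any such change falls entirely on one method.

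The masked CGM rules out CGM feedback as a cause of change between weeks. Other possible causes remain: the age of the sensor, practice or fatigue with the two-week log, and learning from fingersticks. A shared improvement would be reported as a benefit of carbohydrate counting; a shared deterioration would hide a real benefit.

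**Working it through.** **The plan's own figure.** The sample size of 20 cannot be reproduced, because no effect size, SD, power or dropout rate is given. Everything below except the identification step therefore rests on assumed values. They are expressed in SD of the within-patient (week 2 minus week 1) difference, with a two-sided test at 0.05; the plan does not state sidedness.

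**Identification.** Let τ be the method effect (counting minus fixed) and π the average week effect. Every patient has expected difference τ + π. A model for the week means with intercept, method and week has three parameters but a design matrix of rank 2, because method and week are the same column. No analysis of those week means can separate τ from π.

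**Size under the planned test** (n = 20, 19 df). The noncentrality is (τ + π)√20. An effect of 0.66 SD gives about 80% power.

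| Week effect (SD) | Rejection rate, τ = 0 | Power, τ = 0.66, opposing week effect |
|---|---|---|
| 0 | 5.0% | 79.9% |
| 0.1 | 7.1% | 66% |
| 0.2 | 13.6% | 50% |
| 0.3 | 24.7% | 33% |
| 0.5 | 56.5% | 10% |

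For example, at a week effect of 0.3 the noncentralities are 0.3 × √20 = 1.34 and (0.66 − 0.3) × √20 = 1.61.

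**Randomised order, 10 + 10.** The expected differences are τ + π (fixed first) and −τ + π (counting first). Half the contrast is τ, so π cancels. Its standard error is ½ × √(1/10 + 1/10) = 0.224 SD, the same as 1/√20 for the planned test; only one degree of freedom is lost (18 against 19). In 200,000 simulated trials with τ = 0, this test rejected 5.0% of the time at each week effect in the table.

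**Carryover under randomised order.** If a fraction f of the counting effect persists into a later fixed-dose week, the expected estimate is τ(1 − f/2). At τ = 0.66:

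| f | 0 | 10% | 25% | 50% | 100% |
|---|---|---|---|---|---|
| Power | 79.7% | 76% | 69% | 55% | 29% |

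A test of patient totals between the two order groups would detect carryover of 25%, 50% or 100% only 5–6%, 6–8% or 8–18% of the time, for assumed week-to-week correlations of 0.8 down to 0.3.

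**Could the existing data rescue the fixed order?** Daily values would allow a linear day term beside the step at day 8. The two correlate at 0.868, so the variance inflation is 1/(1 − 0.868²) = 4.06 and the standard error doubles (ratio 2.02), if daily errors are independent and account for all the variance of the difference. Power at 0.66 SD then falls to about 28–31%, and the effect detectable with 80% power rises from 0.66 to 1.33 SD. The model removes a linear drift fully and an abrupt change at day 8 not at all. It leaves 60% of a change rising in equal steps on days 6 to 9. For practice that levels off with a 3-day time constant it over-corrects by 30%.

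**The case against.** The strongest reply is that no week effect has been shown. The protocol reports no sensor drift. Prescribing the dosing method for each week limits free dose adjustment from fingersticks, and log fatigue in week 2 is arguably part of what counting does in practice. Study power calls this a proof-of-concept study looking for a trend between two periods. A fixed order also keeps a preceding week of count-based dosing out of the fixed-dose week, whereas randomising brings in carryover that this trial could hardly detect.

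Much of this stands, and it limits how much can be said about size: the rates above illustrate assumed inputs. If the week effect is zero, the test keeps its 5% level, but the design cannot show that. The proof-of-concept label tempers the consequence; it addresses imprecision, not bias, and nowhere does the plan state the order limitation. Training before day 1 and carbohydrate logging in both weeks weaken the case for a fixed order without removing it.

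The day-trend figures also depend on their assumptions. If half the variance of the difference is patient-to-patient variation in the method effect, the standard error ratio is 1.59 and power about 42%. Daily autocorrelation of 0.3 or 0.6 gives variance inflation of 3.08 or 1.88. A ramp starting from zero at day 6 leaves 72%, not 60%. Likewise, carryover merely shrinks a real effect only if it is proportional to that effect; eating habits that persist after counting could bias the contrast otherwise. None of this separates method from week under the planned test.

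**Conclusion.** The concern holds. The confounding is algebraic and needs no outside figure, and confidence in it is high. The bias equals the average week effect, whose size and direction are unknown. Over assumed week effects of 0.1 to 0.5 SD, the false-positive rate runs from 7% to 56%, or power at 0.66 SD falls from 80% to between 66% and 10%. As written, the Hypothesis and Specific Aims claim more than the Methods and Statistical Analysis can deliver. This should be fixed; the exploratory purpose keeps it from being more serious.

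**What to change.** **Preferred.** Randomise the order 1:1, with 10 patients fixed-first and 10 counting-first. For each outcome, compare the week 2 minus week 1 differences between the order groups and take half the contrast as the method effect. Show results by order group as description only, and state that absence of carryover is assumed. The cost is a protocol amendment and a short randomisation list, with no extra patients, sensors or visits. The main downside is the possible loss of power from carryover, since there is no washout.

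**If the order can no longer change.** Report a week 1 to week 2 change that cannot be attributed to the dosing method. Fingerstick values are already to be collected ("From the log, insulin doses and fingerstick glucoses will be collected"), so add CGM-minus-fingerstick differences by day as a supporting check. This addresses sensor drift only, not behaviour, and the plan gives no fingerstick frequency. The day-trend model may be added as a sensitivity analysis with its assumptions stated. This route needs only wording and data already planned.

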#### **Measurement:**

Thorough literature search found only one other study examining inpatient carbohydrate counting. Three other studies were identified that examined other insulin regimens inpatient and their effect on hypoglycemia and hyperglycemia rates. The statistical analysis methods of those studies were used as a benchmark for this study

#### Data Points:

Primary: We will be measuring postprandial excursions on continuous glucose monitoring data and the instances of hypoglycemia during the two-week timeframe of the study period

Secondary: Total carbohydrates consumed each day during the two-week time frame, total daily dose of insulin per 24 hour period (midnight to midnight) will be secondary endpoints

CGM devices can be connected to desktop machines and downloaded via a receiver. The baseline characteristics that will be collected are age, sex, race, exocrine pancreatic function status, CFTR genotype, duration of CFRD, hemoglobin A1c, renal function tests, weight and BMI. From the log, insulin doses and fingerstick glucoses will be collected. The outcome measures that will be extracted from the CGM devices to assess the effectiveness of our intervention in improving glycemic control and nutritional status will include daily glucose trends calculated by percentage of time in target interstitial fluid glucose levels level and percentage of target interstitial fluid glucose levels readings, hypoglycemia episodes, and average glucose from the 2 comparison periods. This data will be compared for statistical significance using student t-test with significance assigned to p-value less than 0.05.

The clinical endocrine fellow will collect data from each included patient by performing a Cerner and Epic (EHR) chart review. Data will be recorded on an encrypted UPMC OneDrive Microsoft excel spreadsheet with password restricted access. A list of collected data points are as follows:

- 1. Age
- 2. Sex

- 3. Race
- 4. Exocrine pancreatic function status (sufficient vs. insufficient)
- 5. CFTR genotypes
- 6. Duration of CFRD
- 7. Weight and BMI at the most recent office visit or on the day of the placement
- 8. Labs: serum creatinine and eGFR (most recent value in the last 12 months), hemoglobin a1c (the most recent value in the last 3 months, or will be performed by point of care testing at the time of the CGM device placement)
- 9. Modulator use: ivacaftor (Kalydeco), lumacaftor/ivacaftor (Orkambi), tezacaftor/ivacaftor (Symdeko), elexacaftor/tezacaftor/ivacaftor (Trikafta); start date and duration of use
- 10. Meal /snack time insulin doses from log
- 11. CGM glycemic control data (percentage of time within glycemic target)
- 12. Data from fingerstick before and after intervention
- 13. Nutritional information with carbohydrates consumed per meal/snack in grams

Study power: This is a proof-of-concept study and we plan to include 20 patients in this study which we expect will be adequately powered to demonstrate a trend and compared intrasubject variation between the 2 study periods.

Controls/patient demographics: Patient demographics are shown in table 1, while variables to be measured are shown in table 2.

## Data safety:

Data for individual patients will be deidentified without names, addresses, DOB, or SSN. Individual patients will be classified as patient 001, 002, 003 etc.

A subject identifier key will be used to match the medical record number with a subject ID number. The subject identifier key will be maintained in a password protected Excel file. Collected information on the data collection tool will be entered into a separate password protected Excel file. One year after the conclusion of the study, all collected data will be destroyed by permanently deleting electronic copies. The principal investigator and study team members will not disclose PHI to any other person or entity.

All individuals involved in the completion of this study will take every precaution to ensure the safety and confidentiality of all patient information. This will include the use of an encrypted UPMC OneDrive Microsoft excel spreadsheet with restricted access. No patient information will ever be stored on personal devices or on an external hard drive/flash drive.

## **Statistical Analysis:**

We will perform a within subjects statistical comparison using student t-test to compare CGM glucose values, time in target glucose level, percent of glucose values in target and hypoglycemia events during each week using the 2 standard methods of meal-time rapid acting insulin dosing. The data will be analyzed by SPSS statistical software package.

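### The after-meal glucose endpoint in Hypothesis 1 and the primary data points is not carried into the stated CGM extraction and test lists, and no meal window or meal-to-week rule is given

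*Combined protocol and SAP*

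**What the plan says.** Three sections make after-meal glucose the object of the study.

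- **Hypothesis** (first item) concerns "postprandial interstitial fluid glucose levels in patients who utilize carbohydrate counting" and expects "improved control as defined as area under the curve and time in target".
- **Specific Aims**, Aim 1, lists three excursion measures: time in target, percent of glucose in target, and "peak post prandial glucose with fixed insulin dosing versus carbohydrate count based insulin dosing".
- **Data Points**, primary: "We will be measuring postprandial excursions on continuous glucose monitoring data and the instances of hypoglycemia".

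Two places say what will be done with the CGM data.

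- **Data Points**, extraction: "daily glucose trends calculated by percentage of time in target interstitial fluid glucose levels level", the matching percentage of readings, hypoglycemia episodes and "average glucose from the 2 comparison periods". The numbered collection list that follows has a single CGM item, percent time within target.
- **Statistical Analysis**: a within-subject Student t-test to "compare CGM glucose values, time in target glucose level, percent of glucose values in target and hypoglycemia events during each week".

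Methods asks patients to keep a paper log of carbohydrate intake at meals and snacks and of insulin doses. It does not say that clock times are written down. The calendar-day insulin total in Data Points implies dated entries, but not timed ones. The section on controls and demographics refers to a table 2 of variables. Neither that table nor the log form is in the text available for review.

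**The concern.** The two study weeks differ in how mealtime insulin is dosed, and the hypothesis is about glucose after those meals. If the extraction and test lists are followed literally, the hypothesis will be answered with figures for the whole day or week. Those figures mix after-meal hours with overnight and between-meal hours.

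Three choices also stay open until the data are in hand: the length of the window, what happens when the next meal or snack falls inside it, and whether AUC is total or measured above the pre-meal level. Each can change the result. Meal times are the one item that cannot be repaired later. If the log form has no place for them, the CGM trace cannot be lined up with meals after the 14-day wear.

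**Working it through.** **1. Follow each measure from hypothesis to test.**

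| Measure | Where named as an objective | In the extraction list? | In the test list? | Tied to meals there? |
|---|---|---|---|---|
| Postprandial AUC | Hypothesis 1 only | No | Not by name | – |
| Postprandial peak | Aim 1 only | No | Not by name | – |
| Time in target | Hypothesis 1, Aim 1 | Yes, daily | Yes, by week | No |
| Percent of glucose in target | Aim 1 | Yes, daily | Yes, by week | No |
| Average glucose / CGM glucose values | – | Yes, per period | Yes, by week | No |
| Hypoglycemia | Hypothesis 2, Aim 2, primary data point | Yes | Yes, by week | Not needed |

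Two of Aim 1's three measures are tested, but by week. Its only explicitly after-meal measure, the peak, is in neither list. No section gives a window, an overlap rule, or a rule for reducing many meals to the one value per patient-week that a paired t-test needs.

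**2. What a whole-week figure shows of an after-meal difference (assumed inputs).** Let *w* be the share of the day inside after-meal windows, *D* the between-week difference inside them, and *f* the difference outside them as a share of *D*. Take windows as non-overlapping and *w* as equal in both weeks. A weekly mean is a time-weighted average, so

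weekly difference = *w·D* + (1 − *w*)·*f·D* = *D*·[*w* + *f*(1 − *w*)].

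The documents give neither windows nor meal counts. I assume a range from 3 windows of 2 h to 5 windows of 4 h:

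- *w* = 3×2/24 = 0.250, up to 5×4/24 = 0.833.
- *f* = 0: 25% to 83% of *D* appears in the weekly figure.
- *f* = 0.5: 0.250 + 0.5×0.750 = 0.625, up to 0.833 + 0.5×0.167 = 0.917.
- *f* = 1: 100%.

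Weekly percent time in target is the same kind of average, so the formula applies to it in percentage points. With *f* = 0, an assumed 20-point after-meal difference appears as 20×0.250 = 5 to 20×0.833 = 16.7 points.

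These figures concern the size of the difference only. Power also depends on the variability of the two summaries, and the plan gives no SD, effect size or numeric power.

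**3. Why the AUC type must be fixed.** Suppose the rise after meals is identical in both weeks, but pre-meal glucose is higher by *X* in one. Time-normalised total AUC then differs by *X*, and incremental AUC by 0. Aim 4, "To compare the effect of two methods of rapid acting insulin delivery on fasting glycemia", shows that the plan itself allows for such a shift. Hypothesis 1 speaks of glucose levels and Data Points of excursions, so the text does not settle which type is meant.

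**4. Are the CGM data sufficient?** Yes. At one reading a minute, a 3 h window holds up to 3×60 = 180 readings, out of 7×24×60 = 10,080 in a week. The gap is in the definition and possibly in the logged meal times.

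**The case against.** The strongest reply is that the test list begins with CGM glucose values. That term is broad enough to take in after-meal AUC and peak, and the reference to each week may only name the two periods being compared. Time in target, one of Hypothesis 1's two measures, is tested. Table 2 or the log form may hold the window and the time column. In a 20-patient proof-of-concept study, one sentence of definition might be thought enough.

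Much of this stands, and it rules out two stronger conclusions that a reader might draw.

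- *That the after-meal hypothesis is not, or cannot be, tested.* The broad wording of the test list, the one-minute CGM data and the two unseen items do not support this. Silence in Methods about clock times does not show that the form lacks them.
- *That the whole-week measures lose power.* If part or all of the effect extends beyond the windows, the weekly mean may be as sensitive or more so. The documents cannot settle the direction, so no power figure belongs here.

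The reply does not supply the definition. A term that could cover AUC and peak does not say which window, which AUC or how meals are combined. Time in target is tested without being limited to after-meal periods. Small size is no reason to leave a primary measure undefined when the plan assigns significance at p below 0.05.

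**Conclusion.** The point holds as a gap between the objective and the stated analysis, and it should be fixed. The after-meal endpoint is named in Hypothesis 1, Aim 1 and the primary data points, but it is not carried into the extraction or test lists. The measures that are listed answer a whole-week question.

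The 25% to 83% range for how much of an after-meal difference a weekly figure would show rests on assumed windows and on no effect outside them. It rises to 100% if the effect lasts all day. Any gain or loss of power cannot be determined from the documents.

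Confidence is medium, because table 2 and the log form were not available and could close part of the gap.

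**What to change.** 1. **Methods.** Unless the log form already does so, require the clock time of each meal, snack and insulin dose. This must be in place before patients start logging.
2. **Data Points and Statistical Analysis.** Define the postprandial primary as the patient-week mean, over logged meals, of time-normalised glucose AUC in one fixed, pre-specified window (for example 0–3 h, truncated at the next logged intake). State before analysis whether AUC is total or incremental. Compare the two weeks with a paired t-test.
3. **Other measures.** Report postprandial time in target, with its numeric range stated (the available text gives none), and postprandial peak in the same windows as secondary. Keep hypoglycemia as the other declared primary and the whole-week measures as supportive.
4. **Reporting.** Give, by week, the number of usable windows and the number of meals without a logged time, since eating and logging habits may differ between the two weeks.

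If table 2 or the log form already holds any of this, carry it into Data Points and Statistical Analysis.

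The cost is at most two time columns on the paper log, some derivation programming and a few sentences of text, with no new device or visit. The downside is slightly more work for patients, and meals without a logged time drop out of the postprandial analysis.
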